6.5 Expected Outcomes

Intervention: After the intervention period begins, postpartum women within the selected CHC sites will be more likely to receive any contraceptive method by two and six months postpartum. We anticipate a minimum absolute increase in contraception use of 15% (from 45% to 60%) and a decrease in short IPI pregnancies from approximately 35% to 20% from before to after the intervention, both of which would have a clinically meaningful impact on the population.

Implementation Process: By the end of Aim 2, we expect the intervention will be implemented successfully at all sites. However, important clinic-level and system-level barriers will be identified at each site. For example, the discharge process likely occurs in slightly different ways in each clinic, which may impact who responds to the alert in the EHR and the efficiency in which the co-scheduling can be accomplished.

All modifications (i.e. custom fields, prompts) within EHR and scheduling software have been built. Participating CHC's have been randomized for the intervention. All sites entered the control period April 1, 2021 and the first site will enter the intervention period August 1, 2021.

7.0 Aim 3 Research Design, Methods, and Data Analysis

Aim 3 is to assess implementation of linked PP contraception and newborn care and report on key barriers and facilitators related to successful implementation of the intervention.

7.1 Outcome Variables

We will utilize the RE-AIM framework to evaluate outcomes of the effectiveness-implementation hybrid trial throughout the trial. Table 3 describes the data collected per RE-AIM construct.

Table 3: RE-AIM Evaluation of Implementation of Linked Care		
RE-AIM Construct	Data Source	Outcome
Reach	EHR	
 Percentage of eligible women identified for a co-scheduled appointment
Effectiveness	EHR	
 Percentage of eligible women receiving any form of contraception at 2 and 6 months PP
Adoption	EHR	
 Percentage of eligible women offered co-scheduled appointments
Implementation	EHR field created for study Key informant interviews	
 Work flow process to identify eligible women in EHR and offer co-scheduled appointments Acceptability and feasibility of the intervention as reported by PP women and clinic staff Barriers or facilitators of implementation that impact fidelity to the intervention as reported by CHC staff and PP women (i.e., length of visits, no shows)
Maintenance	EHR	
 Reach and Implementation outcomes measured at years 4 and 5 of grant

(Adapted from Glasgow et al. 2007)

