The **Reach, Effectiveness, Adoption, Implementation, and Maintenance (RE-AIM) framework** is an evaluation and reporting scheme commonly used to examine the potential public health impact of an intervention.⁴¹ *Reach* represents the number and representativeness of patients who participate out of the eligible patient population. *Effectiveness* is the impact of the intervention on participant outcomes. *Adoption* is the number and representativeness of eligible staff/settings that agree to deliver the intervention out of all eligible staff/settings. *Implementation* is the fidelity to the intervention. *Maintenance* is the degree to which the intervention is sustained over time. RE-AIM provides a useful measurement framework for capturing both clinical and implementation outcomes within the same study. **Integrating CFIR and RE-AIM within a hybrid clinical effectiveness and implementation trial will generate the evidence needed to rapidly translate the findings from a clinical trial of linked care maternal and infant care to standard practice.**

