6.0 Aim 2 Research Design, Methods, and Data Analysis

Aim 2 is to implement linked PP contraception and newborn care in 7 CHCs and evaluate the effect on provision of PP contraception and rates of short-interval pregnancy. We hypothesize that a linked PP contraception care with newborn care model can be implemented successfully in urban and rural CHC settings. PP women offered contraceptive care linked with newborn care would be more likely to receive any form of contraception at two months PP and by six months PP. Additionally, we hypothesize that CHCs will have a lower rate of short IPIs among incoming prenatal patients after implementing the linked contraception care with newborn care model compared with their rate prior to implementation.

Using a novel approach, we will test a patient-oriented alternative delivery system for PP contraception that will fill a gap in our current system resulting in improved contraceptive access for women. We will use a cluster randomized cross-sectional stepped wedge design to test the novel linked contraception and WBV model's impact on increasing PP contraception uptake in urban and rural CHCs, compared to usual care. We will include the 7 CHCs (six urban, one rural) recruited through Aim 1 of this project.

During the intervention period, staff will capture women during the first WBV (typically 3-5 days after delivery) and offer to have the next visit co-scheduled for infant and contraception care. Current practice at all AllianceChicago CHCs is to ensure all newborn infants leave the clinic with the next visit already scheduled. Appointments are scheduled during the discharge process at the end of each visit. During the discharge process all women 0-6 months postpartum who are established patients will be identified by an electronic prompt in the infant's electronic medical record. The prompt will instruct staff to offer the mother a co-scheduled visit for newborn and contraceptive care at the time of the next newborn visit.

Those who agree will be co-scheduled and those who are not in need of care, or do not wish for co-scheduled care, can decline. Women will be excluded if they had a tubal ligation or a long acting reversible contraception planned immediately after delivery. Women will be offered this co-scheduling option at each WBV through six months PP. Repeat opportunities for co-scheduled care are important as women's needs and

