7.2 Data Collection

AllianceChicago's information technology (IT) team will build custom reports in their data warehouse to access and validate data in real-time. Reports will be built to pull data (ICD, CPT and HCPCS codes) from the medical record and billing claims; which will be used to determine implementation success. Reports will be built to monitor: 1) EHR alert consistency; 2) if co-scheduled care is offered; 3) if co-scheduled care is accepted or declined by women; 4) among those who accept, if both the co-scheduled appointments are completed

At approximately the midpoint of each site's intervention period, key informant interviews will be conducted with staff, physicians and PP women to assess implementation

outcomes such as acceptability, feasibility, and fidelity over time. Semi-structured interview guides will be developed around CFIR constructs (similar to Aim 1) to elicit information related to barriers and facilitators encountered during the implementation of linked care and the RE-AIM implementation outcomes listed in Table 3. Interviews will be audio-recorded and transcribed and carefully reviewed by both PIs. If the subject declines to have their interview recorded, they will be asked to complete the interview in person and notes will be taken in lieu of audio-recording.

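### Table 3 measures Reach as women identified and Adoption as women offered a visit, which contradicts the plan's own definitions and leaves participation out of the RE-AIM outcomes

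*Combined protocol and SAP*

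**What the plan says.** Section 4.0 sets out the framework. Reach "represents the number and representativeness of patients who participate out of the eligible patient population". Adoption "is the number and representativeness of eligible staff/settings that agree to deliver the intervention out of all eligible staff/settings".

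Table 3 in section 7.1 then gives the outcome for each construct. Reach is "Percentage of eligible women identified for a co-scheduled appointment" and Adoption is "Percentage of eligible women offered co-scheduled appointments", both drawn from the health record. The Maintenance row repeats the Reach and Implementation outcomes in years 4 and 5 of the grant. Section 7.3 assesses Reach and the record-based implementation outcomes at the midpoint and end of each step's intervention period.

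Section 6.0 describes the workflow. Women "will be identified by an electronic prompt" in the infant's record, the prompt tells staff to make an offer, and the woman then decides: "Those who agree will be co-scheduled and those who are not in need of care, or do not wish for co-scheduled care, can decline".

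Section 7.2 lists monitoring reports that include "if co-scheduled care is accepted or declined by women" and "among those who accept, if both the co-scheduled appointments are completed".

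**The concern.** The plan states what Reach and Adoption mean and then measures something else under the same names. A woman who is identified but never offered a visit, or who is offered one and declines, still counts as reached. The Adoption percentage has women in numerator and denominator, so it cannot say how many staff or clinics took the intervention up. A few could account for most of the offers.

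At stake is what Aim 3 reports. Section 4.0 presents the combined frameworks as the evidence needed to move linked care into practice, and uptake by women is central to that. It also bears on reading Aim 2, because a weak effect on contraception means one thing if few women took up linked care and another if most did. If no listed outcome commits to uptake, its definition and denominator can be chosen after the results are seen.

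**Working it through.** The plan states no figure for Reach or Adoption, so there is nothing to reproduce. The check sets the passages side by side.

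**Step 1. Definition against measure**

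| Construct | Section 4.0 | Table 3 |
|---|---|---|
| Reach, numerator | patients participating | women identified |
| Reach, denominator | eligible patients | eligible women |
| Adoption, numerator | staff or settings agreeing to deliver | women offered a visit |
| Adoption, denominator | eligible staff or settings | eligible women |
| Representativeness | part of both constructs | in neither row |

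Reach has the right denominator and the wrong event. Adoption has the wrong unit throughout.

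**Step 2. Order of events.** From section 6.0 the sequence is eligible, identified, offered, accepted or declined, then visits completed. Identification is the first step after eligibility and participation begins at acceptance. For a given number of women identified, Table 3's Reach is the same whether none or all of them accept.

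**Step 3. Where acceptance and completion go.** Section 6.3 adds a field for a co-scheduled appointment, and section 7.2 plans reports on acceptance and completion. No row of Table 3 names either. The record-based workflow item in the Implementation row covers identifying women and offering visits. Section 7.3 analyses Reach as labelled, and the Maintenance row carries it forward.

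**Step 4. Representativeness.** The only planned comparison of patient characteristics is in section 6.4. It contrasts control-period with intervention-period patients, not participants with non-participants.

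**Step 5. Illustration, with every rate assumed.** Take 95% of eligible women identified, 70% of those offered, 30% to 60% of those accepting, and 50% to 80% of those completing.

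- Table 3 Reach: 95%
- Table 3 Adoption: 0.95 × 0.70 = 0.665, or 66.5%
- Accepted, out of eligible: 0.95 × 0.70 × 0.30 = 0.20 to 0.95 × 0.70 × 0.60 = 0.40
- Completed, out of eligible: 0.95 × 0.70 × 0.30 × 0.50 = 0.10 to 0.95 × 0.70 × 0.60 × 0.80 = 0.32

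These figures show how far the quantities can separate. They do not predict this trial.

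**The case against.** The best defence is that this is a labelling conflict within one aim and no data are lost. Offers, acceptance and completion will all be recorded, section 7.2 ties those reports to judging implementation success, and the Implementation row mentions no-shows. Aim 3 also rests heavily on interviews about acceptability, feasibility and fidelity. All of that is correct. It shows that the repair is cheap, but it does not supply a listed outcome that commits to participation.

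Several stronger readings are tempting and should not be made.

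- *Reach will be close to 100% by construction.* The documents do not establish this. Section 6.0 limits the prompt to established patients while the inclusion criterion in section 6.1.1 does not. Identification depends on matching mother and infant records, and section 7.2 monitors whether the alert is consistent. The percentage may vary and be informative about the prompt, but it still does not measure participation.
- *A null primary result could not be interpreted.* Acceptance and completion will exist and can be examined. What is missing is a prior commitment to how.
- *Adoption merely counts prompts.* Staff must act for an offer to occur, so the row does reflect delivery. Its fault is the unit.
- *Low acceptance means poor reach.* Section 6.0 lets women who do not need care decline, so acceptance has to be read with that in mind.

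**Conclusion.** The point holds on the plan's own text, without any outside definition of the framework. As written, the quantity reported as Reach, and the Maintenance measure that reuses it, would not reflect participation at any value. Adoption would be expressed per woman instead of per staff member or setting, and representativeness would go unreported for both.

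The numerical size of the discrepancy cannot be derived from the documents. The 10% to 32% range rests entirely on assumed rates, and the conclusion does not depend on it.

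The consequence is confined to Aim 3 reporting and to how well Aim 2 can be explained. A reader might infer that the effectiveness result is compromised. It is not: the primary outcome in section 6.2 and its model in section 6.4 do not use Reach or Adoption. The change should be made before Aim 3 results are tabulated.

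**What to change.** Revise Table 3 as follows.

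- **Reach:** percentage of eligible women who accept a co-scheduled visit, with the percentage of eligible women who complete at least one reported alongside. The completion report in section 7.2 is conditional on acceptance, so it needs the eligible-women denominator added. Compare the characteristics of participants and non-participants using data already in the record.
- **Implementation (fidelity):** move the percentages identified and offered here.
- **Adoption:** report by setting, as sites that agreed out of sites identified as eligible during the recruitment described in section 5.0, together with offer rates by clinic. Among the seven recruited sites alone, agreement would say little, so the wider denominator matters. Add staff-level Adoption only if the record captures who made each offer. The documents describe fields for whether a visit was offered or co-scheduled and do not say who offered it, so the sponsor should confirm this first.
- **Maintenance:** carry the redefined Reach and Implementation measures into years 4 and 5.

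The cost is a change of table wording, a little more analysis, and probably a less favourable Reach figure. Acceptance and completion reports are already planned, so Reach needs no new data collection. Staff-level Adoption is the one element that could require a new field, since section 6.5 says the custom fields are already built.

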7.2 Data Collection

AllianceChicago's information technology (IT) team will build custom reports in their data warehouse to access and validate data in real-time. Reports will be built to pull data (ICD, CPT and HCPCS codes) from the medical record and billing claims; which will be used to determine implementation success. Reports will be built to monitor: 1) EHR alert consistency; 2) if co-scheduled care is offered; 3) if co-scheduled care is accepted or declined by women; 4) among those who accept, if both the co-scheduled appointments are completed

At approximately the midpoint of each site's intervention period, key informant interviews will be conducted with staff, physicians and PP women to assess implementation

outcomes such as acceptability, feasibility, and fidelity over time. Semi-structured interview guides will be developed around CFIR constructs (similar to Aim 1) to elicit information related to barriers and facilitators encountered during the implementation of linked care and the RE-AIM implementation outcomes listed in Table 3. Interviews will be audio-recorded and transcribed and carefully reviewed by both PIs. If the subject declines to have their interview recorded, they will be asked to complete the interview in person and notes will be taken in lieu of audio-recording.

7.3 Data Analysis

Reach and implementation outcomes from the EHR will be assessed at the midpoint and endpoint of the intervention period for each step. Qualitative data will be coded according to CFIR constructs. Data will be coded independently by two coders and then discussed to resolve coding discrepancies. Emerging themes will be identified and categorized by CFIR construct and/or implementation outcome: acceptability, feasibility, and fidelity. Mixed methods will be used to elaborate on quantitative RE-AIM findings with themes from qualitative data.⁵⁶

7.4 Expected Outcomes

We expect to identify important barriers and facilitators as a continuum during the implementation process at the clinician-level, clinic-level and system-level. Understanding those factors could help not only to improve the intervention at the local CHCs, but also will could increase understanding of similar interventions in the CHC setting. Findings will also result in understanding factors that may differ between urban and rural settings. Determining how implementation in CHCs vary over levels of urbanicity will be a valuable contribution to the literature. The process and results of this aim will be disseminated to contribute to the implementation science literature.

8.0 Expected Risks/Benefits

Potential risks consist of potential breaches of confidentiality. However, participants will be allowed to opt out of the study at any time and to not respond to questions they are uncomfortable with, without any penalty. Study records that identify the participant will be kept confidential; however there is a risk of loss of confidentiality. Participants will be informed of these risks, protections against loss of confidentiality, and their rights to skip any question and to withdraw from the study at any time in the consent forms and all relevant study documents. We will take the utmost caution to protect the confidentiality of responses.

The potential benefits of this research far outweigh the risks. Pregnancies conceived within 18 months of a prior delivery (termed short inter-pregnancy interval) place mothers and infants at high risk for poor health outcomes including pre-eclampsia, anemia, and

preterm birth. Despite these negative health consequences, nearly one third of women experience a short inter-pregnancy interval highlighting a significant public health problem in the U.S. A critical approach to preventing short inter-pregnancy intervals is to provide postpartum women with timely access to contraception. The current standard clinical practice is to have women return six weeks after delivery for a PP visit at which time contraceptive needs are addressed. However, many women resume sexual activity prior to six weeks PP, and many women, particularly low-income minority women do not present for this visit. Thus, there is an urgent need for patient-centered approaches to improve timely access to PP contraception to improve outcomes for women and children. This study has the potential to address these unmet contraceptive needs of postpartum women using a patient-centered approach to contraception care.

The key informant interviews will allow us to effectively develop and implement a linked postpartum and newborn care in CHCs and in turn, compare clinic-level provision of all methods of contraception and clinic- level rates of short inter-pregnancy intervals. The intervention and assessments will allow us to understand how well this intervention works and provide critical feedback in a real-world setting. The possible risks (i.e. potential confidentiality breaches) are outweighed by the new knowledge gained regarding how to implement this patient-centered model intervention in both urban and rural CHC settings. We have adequate safeguards to protect against these risks and will alert the RUMC IRB of any problems.

9.0 Data Collection and Management Procedures

We will collect qualitative and quantitative data from participants via audio-recorded and transcribed key informant interviews administered via laptop computer, telephone, and/or paper-and-pencil evaluations. Additionally, clinic-level EHR data will be collected pre- and post-implementation of the intervention.

Subjects will be assigned a study ID during the course of the study. All data collected will use the participant's study number in place of identified information. Participant information will be de-identified and will not be linked to any specific subject. The consent forms will be the only remaining link to the subjects. They will be available only to the IRB-approved research team. Given reliance agreement between collaborating institutions, consent forms for the subjects will be securely stored in a locked filing cabinet in a locked office within a PI's institution (i.e. Rush University Medical Center [RUMC], University of Illinois at Chicago [UIC]). All data will be stored on a secure, password- protected computer accessible only to the study team.

A reliance request on behalf of UIC and AllianceChicago was approved in July 2021. This reliance agreement is being submitted to RUMC's Institutional Review Board (IRB) and once approved, the RUMC's IRB will be the IRB of Record. Additionally, data from this study will be shared between collaborating sites (i.e., RUMC, UIC, AllianceChicago). A confidentiality agreements are in place and a data sharing agreement will be submitted and approved prior to any data being shared between sites.

10.0 Quality Control and Quality Assurance

Analysis of each phase will help to ensure adherence to the protocol as well as informing the next phase of the research project. The co-investigators are all responsible for ensuring the quality of the data and how the analysis will inform the next phase of the research study.

11.0 Data and Safety Monitoring

The PIs and Co-Is are responsible for monitoring the data, assuring protocol compliance, and conducting safety reviews regularly. The research staff will oversee day-to-day compliance. This protocol presents minimal risks to the subjects and adverse events or other problems are not anticipated. The PIs, Co-Is, and research staff will be responsible for monitoring the data, assuring protocol compliance, and conducting safety reviews at regular intervals, which must be conducted at a minimum of every 6 months (including when re-approval of the protocol is sought). During the review process, the PIs, Co-Is and research staff will evaluate whether the study should continue unchanged, require modification/amendment, or to close enrollment. The PIs, Co-Is, IRB, and research staff will ensure that any deviations from the protocol or safety concerns are reported according to institutional guidelines. Data and study risk will be assessed throughout the study.

12.0 Regulatory Requirements

12.1 Informed Consent

A qualified member of the study team will conduct eligibility screening to ensure participant eligibility. Eligible participants will be consented and enrolled. Recruitment will take place at the participating CHC sites. The informed consent process will inform the participant that participation in the study is completely voluntary.

